Effects of Reducing Indoor Air Pollution on the Adult Asthmatic Response (INHALE 2)

NCT02153359

07/31/2019

Study Protocol and Statistical Analytical Plan

Title: The Effect of Reducing Air Pollution on the Adult Asthmatic Response (INHALE2)

Abstract

Asthma is one of the most common chronic diseases in adults, and inner-city residents, who typically live in poorly maintained urban housing, suffer a disproportionate burden of asthma morbidity (1). Many factors contribute to this disparity, including the observation that the urban indoor environment has been shown to have higher concentrations of indoor air pollutants than suburban counterparts (2). An increasing amount of evidence has shown that air pollutants, which contain particulate matter, including coarse (PM_{2.5-10}) and fine (PM_{2.5}) particles, are associated with greater respiratory morbidity in asthmatics (3-9). While the bulk of this data focuses on ambient air pollution, accumulating evidence suggests that indoor air pollution, which (unlike outdoor pollution is not EPA regulated) may be even more harmful (10). Moreover, exposure to these pollutants may be prolonged, as Americans spend most of their time indoors (11). Fortunately, the indoor environment is more amenable to modifications by the individual, thus making it an attractive target for interventions aiming to improve asthma health.

One such intervention is introduction of a HEPA air cleaner. We have previously shown that introduction of a HEPA air cleaner results in sustained improvements in indoor pollution concentrations and respiratory symptoms (12,13). Our prior work has investigated the effects of indoor particulate matter on biological and clinical markers of respiratory health in a cohort of inner city children in Baltimore. However, given the age of our participants and research procedure restrictions, we have been limited by the inability to collect bronchoscopic specimens, which could reveal important information regarding lung-specific immune responses within the lower airway. The aim of this project is to extend these findings to a population of urban non-smoking adults with asthma, and characterize both local and systemic responses to the indoor environment. In addition, we hypothesize that actively removing these pollutants through an air cleaner intervention will attenuate their impact on asthma morbidity. This study, INHALE 2, extends evaluation of a subgroup of participants from a parent study, INHALE 1.

In the parent study, 100 adult subjects will be studied longitudinally during a 1-week period at baseline and again at 3 months, during which environmental monitoring of indoor air quality, as well as health assessments (respiratory symptoms, lung function and serum markers) will be conducted. As part of this initial study, we aim to further characterize the inflammatory and oxidative stress pathways that have been implicated in the airway's response to PM in the published literature. To this end, markers in the blood, will be analyzed and linked to changes in indoor particulate matter. Subsequently, a subset of 40 subjects from this cohort that meet safety criteria will then be randomized to having one of two interventions—HEPA air cleaners or sham air cleaners—placed in the home for 1 month's duration. After this month, the true or sham air cleaner will be removed from the home, and no machines will be present in the home for at least another month (washout period). In the final month of this study, the two intervention arms will be crossed over in a blinded fashion, and true/sham air cleaners will be placed in the home again for 1 month. During the first and third months, homes will undergo continuous environmental monitoring and participants will undergo personal environmental monitoring, along with simultaneous health assessments that include questionnaires, diaries, lung function testing, and blood testing. In addition, during the last week of each month with the intervention, participants will undergo bronchoscopy, during which we will obtain airway samples in order to compare lower airway response to the interventions.

In summary, more evidence is needed to understand the local pulmonary and systemic mechanisms that contribute to the burden of asthma in susceptible populations such as urban dwellers exposed to high levels of indoor pollution. Furthermore, by examining the potential alleviating effect of actively reducing chronic exposure to air pollution in the indoor environment, we aim to strengthen the causal relationship between PM and worsening asthma. Such evidence has the promise to lay the groundwork for future clinical recommendations and public policies for environmental control practices.

Objectives (include all primary and secondary objectives)

Primary Objective:

The aim of this project is to investigate the effects of an air cleaner intervention, compared to sham air cleaner, on the change in indoor air pollution, notably fine and coarse particulate matter (PM), in the home of adult asthmatics.

Secondary Objectives:

We will also investigate the effects of an air cleaner intervention, compared to sham air cleaner on clinical markers of asthma health, specifically day and nighttime symptoms, medication usage, and asthma-related quality of life using questionnaires. The effects on lung function using spirometry and alterations in airway and systemic biomarkers of inflammation will also be explored. Finally, the effects of the intervention compared to sham on the indoor air nicotine concentration will be assessed.

Background

The mechanisms by which indoor air pollution potentially worsens asthma morbidity are unclear. In epidemiologic studies, higher indoor PM levels have been associated with increased respiratory symptoms, decreased lung function, and more frequent rescue medication use. Potential mechanisms behind this observed relationship have been investigated in numerous studies, but these have largely been limited to animal models, *in vitro* systems, or human challenge models that high experimental loads of PM. Regardless, these studies have demonstrated that exposure to air pollutants triggers the release of specific cytokines (IL-6, IL-8) which play a central role in cell-to-cell communication, stimulating immune cells, and regulating inflammatory processes within lung tissue, and that this effect is potentiated in patients with asthma. Such inflammatory effects have been demonstrated in bronchoalveolar lavage fluid and cultured bronchial epithelial cells, but also been shown to generate systemic inflammatory responses (as evident by elevated circulating levels of IL-6 and TNF α , as well as CRP), suggesting that inflammation is one of the main responses to PM. However, because this proposal investigates the effect of exposures in the native environment of human subjects, it will provide the opportunity to corroborate these findings in a real-world scenario. Furthermore, this study is novel in that it will investigate the effects of pollution abatement and examine the effect on these asthmagenic processes when real-time PM exposure is actively reduced.

A number of preliminary studies conducted by our group set the stage for this proposal(1). We have extensive experience performing environmental monitoring within Baltimore city and have found that the city has high levels of biologically active indoor PM. In our prior cohort study of 150 asthmatic children, the mean (\pm SD) indoor PM concentration for PM_{2.5-10} (coarse) was $17.4 \pm 21.1 \mu\text{g}/\text{m}^3$ and for PM_{2.5} (fine) was $40.3 \pm 35.4 \mu\text{g}/\text{m}^3$, both of which were significantly higher than the average ambient measurements made over the same time period ($10.3 \pm 21.0 \mu\text{g}/\text{m}^3$ and $12.4 \pm 6.2 \mu\text{g}/\text{m}^3$; $p < 0.01$ for both comparisons). Eighty-five percent of homes had indoor levels of PM_{2.5} exceeding the EPA limit for ambient pollution (2, 14). In addition, we found that this indoor pollution is associated with increased asthma morbidity. Specifically, each $10 \mu\text{g}/\text{m}^3$ increase in PM_{2.5-10} was associated with increases of 8% in the number of days of symptoms

[figure not shown]
severe enough to slow activity, 8% in nocturnal symptoms, 11% in wheezing that limited speech, 6% in rescue medication use, and 6% in overall asthma symptoms (3). We have successfully reduced these in-home PM levels in our prior experience with HEPA air cleaners. In a randomized controlled trial of home environmental interventions in urban Baltimore children with asthma, concentrations of PM₁₀ decreased 30% compared to the control group after 6 months of air cleaner use (12). Asthma symptoms also significantly decreased over this time period. A subsequent study of air cleaners in urban homes of children with asthma showed similar improvements in fine and coarse PM after 6 months, along with improvement in symptom-free days compared to a control group (13). Therefore, we have demonstrated that HEPA air cleaners are able to reduce PM and improve asthma health in inner city children with asthma. However, this has not yet been investigated in adults, and we also do not have an understanding of the biological mechanisms behind such an improvement in asthma symptoms (4). Lastly, our collaborators in the basic sciences have demonstrated that particulate matter has measurable effects on epithelial barrier function, showing that a single dose of PM (150 µg/ml) is associated with enhancement of barrier function and decreased permeability, but repeated exposures result in barrier disruption and increased permeability (15). This evidence supports the hypothesis that chronic pollution exposure can induce the natural airway epithelial barrier to become more leaky, allowing further entry of PM or allergens and triggering further inflammation.

Currently, our research group is actively involved in gathering and analyzing environmental and health data from questionnaires, serum, urine, and exhaled breath samples in children with asthma in several Baltimore studies, and this study will draw upon this expertise, especially with regard to study protocols and operation of equipment. Our field workers have many years of experience in recruiting both children and adult participants with asthma in inner city Baltimore. Furthermore, colleagues in our division are currently engaged in research bronchoscopy in order to collect lower airway samples for their respective studies, and we will be modeling our protocols after these established studies.

Study Procedures

Study design:

Figure 1. Study design

Eligible participants for this protocol will be recruited from the community and health care facilities. All study procedures will be performed as part of this research proposal, with none of the investigations part of routine care. However, clinically significant study results will be shared with participants as needed.

Over the course of 3-5 years, 40 participants that meet criteria will be recruited from the parent study (INHALE 1) which occurs over a 3 month period, and enrolled for an additional months of investigations (i.e. this study will pick up immediately after the parent study leaves off). Informed consent will be obtained at the beginning of the parent study, and hereafter, the participant will be enrolled in both INHALE 1 and INHALE 2 studies, though study procedures for Inhale 2 will not commence until the study period of INHALE 1 is completed.

The study period is broken up into 1st, 2nd, and 3rd assessment periods. During the first month, assessments of each participant's indoor air quality will be accomplished by environmental monitoring of air pollution (PM, nicotine) inside the home. During this month, either true or sham air cleaners will be placed for the entire duration of the month (see figure 1). To measure the air cleaner use compliance, air cleaners will be outfitted with a HOBO data logger, Onset Corporation (Bourne, MA) that has been exempted by Clinical Engineering. Participants will be blindly randomized into receiving one or the other during this time. During the last week of the month, health assessments will be conducted, which include in-home health questionnaires, symptom-, and activity- diaries/recalls, blood, and handheld spirometry. Participants will also be asked to wear a light backpack with air monitoring devices during the course of the day during the last week in order to measure their exposures to pollutants. Finally, at the end of the month, participants will be asked to report to the Johns Hopkins outpatient endoscopy suite for bronchoscopy, during which airway sampling will occur under conscious sedation.

Bronchoscopy: Women of childbearing age will have a repeat pregnancy test (one is already performed in the parent study) during the first month of the study to ensure eligibility as pregnant subjects would be excluded from the study). All bronchoscopies will be performed at the Johns Hopkins Hospital Endoscopy Suite, and will be consented again for the bronchoscopy on the appropriate Johns Hopkins Endoscopy Procedure consent form. Participants who meet safety criteria (including $FEV_1 > 60\%$ predicted) will fast at least 8 hours prior to the procedure and conscious sedation will be administered in accordance to Conscious Sedation Guidelines using intravenous anxiolytics. All participants will have

peripheral blood drawn and nasal rinse prior to bronchoscopy. Subjects will undergo a research fiberoptic bronchoscopy procedure with BAL fluid collected following instillation of room temperature saline in the lung. BAL and blood will be processed for the measurement of cell count and inflammatory mediators. Weekly telephone calls and home visits will occur throughout the study as needed to trouble-shoot and perform quality checks for the study.

At the completion of the first month, the subjects will enter a wash out period of at least 1 month, during which there are no interventions or assessments made. After the wash out period, the subjects will then cross over with regard to the air cleaner-sham cleaner intervention and receive the opposite intervention. During the last month of the study period, all study procedures from the 1st month are repeated. The study is concluded after the completion of the repeat bronchoscopy.

Subjects and study staff will be blinded to whether a true or sham air cleaner is randomly assigned to each home. This blinding is to reduce bias on the part of researchers and participants. Due to the crossover design, each participant serves as his/her own control. Since all participants receive the true air cleaner for one month of the study, they are not deprived of any potential benefits of the air cleaner.

1. Inclusion/Exclusion Criteria

Inclusion Criteria:

1. Age 18-50 years of age
2. Non-smoker (<100 cigarettes in lifetime)
3. Physician diagnosis of asthma
4. Symptoms of asthma and/or reliever medication use in the past 6 months
5. Living in the current residence >= 6 months within Baltimore

Exclusion Criteria:

1. Current diagnosis of another major pulmonary disease, other significant morbidity
2. Pregnancy (as defined by a positive urine pregnancy test at screening of all women of child-bearing potential)
3. Planning to relocate residence or activity that necessitates travel away from home for prolonged period of time during the study period
4. Current use of an air cleaner in the home

2. Study Statistics

A. Primary outcome variable

The change in concentration of fine and coarse particulate matter (PM_{2.5} and PM_{2.5-10}) with the intervention of an air cleaner, compared to sham air cleaner.

B. Secondary outcome variables

1. Asthma control will be compared between the intervention and sham groups. This will include evaluation of changes in respiratory symptoms from self-reported diaries, asthma morbidity and asthma-related quality of life from questionnaires.

2. In addition, we will assess the effects of the intervention compared to the sham on other markers of asthma health. This includes lung function as measured by spirometry, and biomarkers of inflammation as measured in the blood and the lower airways via bronchoscopy.

3. Finally, we will assess the effects of the intervention compared to the sham on the indoor air nicotine concentration.

C. Statistical plan including sample size justification and interim data analysis.

We aimed to enroll 40 participants in this crossover design in order to detect with 80% power (and an alpha of 0.05) a 40% difference in PM concentrations between groups, accounting for an ultimate drop out/loss to follow up rate of approximately 10-15%. The estimate in sample size was based on a prior study from Butz et al. (18), which showed that a sample size of 77 participants was adequate to detect a 44% difference in PM concentrations between the intervention and control groups. [Note that over the course of the study, the planned sample size of 40 was not attained due to difficulties with recruitment. Only patients in the parent observational study willing to undergo bronchoscopies were recruited, resulting in a total of only 23 patients followed, with 2 lost to follow-up by the end of the study.]

A descriptive analysis will be performed with calculation of means, standard deviations, and medians for continuous variables and proportions for categorical variables. Bivariate analyses to assess differences before and after the intervention in each group will be conducted using t-tests or the Wilcoxon rank-sum test for continuous variables and χ^2 or Fisher's exact test for categorical variables.

Citations:

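### The repeat pregnancy test is timed to the month, not to the sedated bronchoscopy, so a compliant result can be up to about 30 days old at the procedure

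*Combined protocol and SAP*

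**What the plan says.** All references are to the combined protocol and SAP.

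- **Repeat test (Study Procedures, Bronchoscopy paragraph).** Women who could become pregnant "will have a repeat pregnancy test (one is already performed in the parent study) during the first month of the study to ensure eligibility". The sentence goes on to give the reason: a pregnant participant would be excluded.
- **Timing of bronchoscopy.** The Abstract says that "during the last week of each month with the intervention, participants will undergo bronchoscopy". The Study design text says "Finally, at the end of the month, participants will be asked to report" to the endoscopy suite.
- **Sedation (Bronchoscopy paragraph).** "conscious sedation will be administered in accordance to Conscious Sedation Guidelines using intravenous anxiolytics".
- **Second period (end of Study Procedures).** After "a wash out period of at least 1 month, during which there are no interventions or assessments made", participants cross over. "During the last month of the study period, all study procedures from the 1st month are repeated".
- **Exclusion criterion 2.** "Pregnancy (as defined by a positive urine pregnancy test at screening of all women of child-bearing potential".
- **Parent study (Study design).** Participants are "recruited from the parent study (INHALE 1) which occurs over a 3 month period", and INHALE 2 follows directly.

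**The concern.** The repeat test is meant to keep pregnant participants out of the study, and its place at the head of the Bronchoscopy paragraph ties it to that procedure. Its only timing rule, however, is a calendar month, and the procedure falls at the end of that month. Staff could follow the rule exactly and still hold a result that is several weeks old when sedation is given.

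What is at stake is participant safety. The Study design text states that none of the investigations are part of routine care, so the sedation and lavage are done for research alone. Participants are aged 18 to 50, so child-bearing potential is relevant. A participant whose pregnancy began, or became detectable, after an early-month test could be sedated and lavaged without anyone having departed from the stated test window. Power, the PM outcome and the treatment comparison are not affected.

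**Working it through.** The plan gives no figure for the age of the test result, so there is nothing to reproduce. The check is date arithmetic.

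**Inputs**
- Test day *d*: any day of the intervention month up to the procedure (Bronchoscopy paragraph).
- Bronchoscopy day *b*: any day in the last 7 days of the month (Abstract), or its end (Study design).
- Month length *m*: 28 to 31 days. This is an assumption, because the document gives no day count.

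**Formula.** Age of the result at bronchoscopy = *b* − *d*.

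**Shortest.** Test on the day of the procedure: *b* − *b* = 0 days.

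**Longest.** Test on day 1 (*d* = 1). The last week runs from day *m* − 6 to day *m*, so the age runs from (*m* − 6) − 1 to *m* − 1.

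| Month length | Procedure on first day of last week | Procedure on last day |
|---|---|---|
| 28 days | 22 − 1 = 21 | 28 − 1 = 27 |
| 30 days | 24 − 1 = 23 | 30 − 1 = 29 |
| 31 days | 25 − 1 = 24 | 31 − 1 = 30 |

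The compliant range is 0 to about 30 days, and 21 to 30 days for a day-1 test.

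**Second bronchoscopy.** The first month's procedures are repeated in the last month, so the test recurs with the same window and the same range. The washout length does not enter.

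**Does other text shorten the interval?**
- Exclusion criterion 2 relies on the screening test, which is earlier still. If screening took place at the start of the 3-month parent study (an assumption), that result is about 3 months old when INHALE 2 begins.
- The washout contains no assessments.
- The pre-procedure steps in the Bronchoscopy paragraph are procedure consent, an FEV1 threshold, a fast of at least 8 hours, a blood draw and a nasal rinse. The fast has a stated interval. The pregnancy test does not.

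**With a same-day test:** 0 days at both procedures.

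**Tests per woman of child-bearing potential within INHALE 2**
- Now: 1 in the first month + 1 in the last = 2.
- Re-time both to the bronchoscopy days: 2, so +0.
- Keep the early first-month test, add one at the first bronchoscopy, and move the last-month test to the second: 3, so +1.
- Keep both early tests and add one at each bronchoscopy: 4, so +2.

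These are calendar gaps, not risks. The document gives neither a pregnancy rate nor the number of women of child-bearing potential, so the number affected cannot be estimated.

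**The case against.** The case against has real weight.

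- **Known pregnancy is already barred.** The exclusion reason in the Bronchoscopy paragraph is not limited to screening or to a test date. A reader might infer that the protocol would let a woman known to be pregnant proceed. It would not. This stands, and it narrows the point to undetected pregnancy.
- **The text leans towards a test near the procedure.** The test opens the Bronchoscopy paragraph, and the health assessments, including blood, fall in the last week. A test done with them would be at most *m* − (*m* − 6) = 6 days old. Nothing suggests that day-1 testing was the schedule. This stands as a caution: about 30 days is the edge of what is allowed, not a description of practice. The sentence still permits it.
- **Other rules may close the gap.** Sedation follows separate guidelines, there is a separate procedure consent, and the Background says the bronchoscopy protocols are modelled on established studies. The study design figure was not visible for this check and may carry visit timing. Any of these could bring a closer test. This limits the claim to the text that can be read.
- **It is a matter of preference.** No interval is laid down anywhere in the document, and a screening test and two repeats already exist. This is partly fair. Still, the stated window does not secure its own stated purpose on the day of sedation, which is more than a missing detail.

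Two stronger readings are tempting and are not supported. One is that the second bronchoscopy goes untested. The sentence on repeating the first month's procedures does not name the test, but its plain meaning includes it. The other is that pregnancy is left out of the bronchoscopy safety criteria. Those criteria are given as an open list with one example, so nothing follows from its absence.

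**Conclusion.** The point holds in a limited form. Within each intervention month, the plan allows a pregnancy test result that is 0 to about 30 days old at a sedated bronchoscopy. A day-1 test gives 21 to 30 days. A pregnancy that begins or becomes detectable in between could be missed.

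The conclusion rests on three things: months of 28 to 31 days, bronchoscopy in the last 7 days of the month, and the plain reading that the test is repeated in the last month. The choice of month length or of day within the last week moves the upper figure between 21 and 30 days and does not change the conclusion.

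A reader might infer that participants in this trial were in fact sedated on stale results. The document does not show that, because it reports neither when tests were done nor what the endoscopy suite required. This is a cheap improvement, for participant safety only. Section 2.C reports that 23 participants were followed and 2 were lost by the end of the study, so the point concerns the protocol text and any re-use of it. Confidence is medium, because local rules could already supply the missing interval.

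**What to change.** Add to the Bronchoscopy paragraph: *Women of child-bearing potential will have a urine pregnancy test on the day of each of the two bronchoscopies, and a negative result is required before sedation.* Name this test among the procedures repeated in the last month. If local endoscopy or sedation rules already require it, say so there.

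An early first-month test may be kept as an eligibility check, since the screening result may be about 3 months old by then. Leave the screening test and the pregnancy exclusion as they are.

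The cost is 0 to 2 extra urine tests per woman of child-bearing potential, depending on whether the existing tests are moved or kept. No new visit is needed, because participants already attend for bronchoscopy and have blood drawn beforehand. The other downside is an occasional withdrawal at the bronchoscopy visit, after the intervention month has been completed.

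### The primary outcome is a change in PM with no stated baseline, and the planned before/after analysis does not fit a crossover with no reading just before the second device month

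*Combined protocol and SAP*

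**What the plan says.** Section 2, Study Statistics, part A of the combined protocol and SAP gives the primary outcome as "The change in concentration of fine and coarse particulate matter", cleaner compared with sham. It states no baseline, averaging window or summary measure. Part C gives descriptive statistics and one inferential plan: pre- versus post-intervention comparisons within each group. That plan covers continuous and categorical variables alike and does not single out PM.

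The measurement schedule is spread over three places:

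- Abstract, parent study: participants are "studied longitudinally during a 1-week period at baseline and again at 3 months", with indoor air monitoring in those weeks. Study Procedures adds that INHALE 2 follows on directly from the parent study.
- Abstract and Study Procedures, device months: "During the first and third months, homes will undergo continuous environmental monitoring". In the first of these, "either true or sham air cleaners will be placed for the entire duration of the month". For the second, "During the last month of the study period, all study procedures from the 1st month are repeated".
- Study Procedures, between the device months: a "wash out period of at least 1 month, during which there are no interventions or assessments made".

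**The concern.** A change needs a reference value, and a before/after analysis needs a *before* reading in each period. The schedule supplies no device-free home reading just before the second device month. An analyst who follows part C as written must take the reference from elsewhere, and the parent study's 3-month week is the only recent device-free reading. It is adjacent to the first device month but not to the second. In the second period, any movement in PM since that week (season, cooking or heating habits, carryover) would be reported as part of the before/after result for whichever device was then in the home.

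There is also a mismatch of question. Two separate before/after results, one for the cleaner and one for sham, do not test the difference between them. That difference is the stated objective and the quantity for which the trial was sized.

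**Working it through.** **The plan's own figure.** The sample size of 40 (80% power, alpha 0.05, 40% difference, 10-15% dropout) cannot be reproduced, because neither an SD for the within-home difference nor a within-home correlation is given. This point does not rest on it. What matters is that it targets a difference in PM levels between cleaner and sham, which needs no baseline.

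**Step 1: which readings exist.**

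| Time | Device in home | Home PM reading |
|---|---|---|
| Parent study, 3-month week | none (current air cleaner use is an exclusion) | yes |
| Month 1 | true or sham, whole month | continuous |
| Washout, at least 1 month | none | none |
| Final month | the other device | as month 1 |

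Age of the parent reading when the second device starts: 1 device month + at least 1 washout month = at least 2 months. No upper limit on washout is given.

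**Step 2: before/after result within each condition, with the parent reading as baseline.** Assumptions: the cleaner multiplies PM by 0.6 (the plan's 40%); sham does nothing; the background level in month 1 equals the parent reading; the background level in period 2 is d times the parent reading; half the homes are in each sequence. On the log scale, averaged over homes:

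- sham change = 0.5 × ln(d)
- cleaner change = ln(0.6) + 0.5 × ln(d)

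| d (assumed) | Sham | Cleaner | Cleaner/sham ratio |
|---|---|---|---|
| 1.2 | √1.2 = 1.095, or +9.5% | 0.6 × 1.095 = 0.657, or -34.3% | 0.657/1.095 = 0.60 |
| 1.5 | √1.5 = 1.225, or +22.5% | 0.6 × 1.225 = 0.735, or -26.5% | 0.735/1.225 = 0.60 |

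Each single-condition figure is off. The ratio is not.

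**Step 3: why the ratio survives.** For a home with log PM of A in the cleaner month, S in the sham month and B at the parent reading, (A - B) - (S - B) = A - S. The baseline drops out exactly, whatever its age.

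**Step 4: why a period term is still needed.** Drift between the two device months cancels from the unadjusted mean of A - S only if the sequences are equal in size. The note in part C reports 23 followed and 2 lost, so 21 completers. The split is not given; the nearest to even is 11 and 10. The unadjusted mean is then ln(0.6) ± ln(d)/21:

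- d = 1.2: 0.182/21 = 0.0087, giving -39.5% or -40.5%
- d = 1.5: 0.405/21 = 0.0193, giving -38.8% or -41.1%

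These errors are small, would grow with a less even split, and are removed by a period term.

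**Step 5: would a second baseline have been better?** With equal correlation ρ between readings, Var(A - S) = 2σ²(1 - ρ). Subtracting a separate baseline in each period gives 4σ²(1 - ρ), twice as large. For illustration only, take the child-cohort fine PM figures in Background (mean 40.3, SD 35.4), so that the difference is 0.4 × 40.3 = 16.12, with 36 evaluable homes (40 less 10%) and a two-sided test. At ρ = 0.5:

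- direct contrast: SE = 35.4 × √(1/36) = 5.90; 16.12/5.90 - 1.96 = 0.77; power 78%
- two subtracted baselines: SE = 35.4 × √(2/36) = 8.34; power 49%
- period-1 change scores only, 18 homes per condition: SE = 35.4 × √(2/18) = 11.8; power 28%

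For ρ from 0.3 to 0.7 the ranges are 64-94%, 37-70% and 21-42%. The SD and ρ are assumptions.

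**The case against.** The strongest reply is that the endpoint already means the within-home cleaner-sham difference. Its full wording is "The change in concentration of fine and coarse particulate matter (PM_{2.5} and PM_{2.5-10}) with the intervention of an air cleaner, compared to sham air cleaner". The primary objective is framed against sham, Study Procedures presents each person as their own control, and the sample size concerns a difference in levels. On that reading continuous monitoring in both device months supplies everything required, and the part C sentence is generic text not aimed at PM. This largely stands. It shows that the trial collected what it needs and that the contrast it was sized for is sound. It does not settle the point, because the only analysis actually written down is a different one and the word *change* is left undefined.

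A reader might go further and infer that the change cannot be calculated in the second half of the crossover. The documents do not support that: the parent study's 3-month reading precedes both device months, and only a reading *just before* the second is missing. A reader might also infer that the effect would vanish because early device days would serve as the baseline. No section proposes this.

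One uncertainty remains. Study Procedures speaks of three assessment periods, which sits oddly with a washout without assessments, and the study design figure is not available here. The washout sentence itself is explicit.

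**Conclusion.** The point holds as a defect in the definition of the primary outcome and in its stated analysis, not as a loss of data. The before/after analysis as written has no contemporaneous reference in period 2. With 20% to 50% upward drift and balanced sequences, it would show sham at +9.5% to +22.5% and a truly 40% effective cleaner at -34% to -26%; downward drift would act in the opposite direction. These figures rest on the assumed drift and effect, since the documents give no period-2 background level.

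It would be tempting to read them as bias in the primary comparison. They are not: the cleaner/sham ratio is 0.60 in every case. What needs correcting is that the plan allows single-condition results to be reported as primary in place of the contrast the design supports.

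**What to change.** In section 2, part A, define the primary outcome as each home's mean PM2.5 and mean PM2.5-10, on the log scale, over the same stated post-installation days in the true and sham months. In part C, compare them within home, cleaner against sham, with a period term. Remove the pre/post comparison for PM, and report the parent study's 3-month reading only as a description of starting levels.

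The note in part C shows that follow-up has ended, so a washout reading can no longer be added. Step 5 shows that the contrast does not need one. Date the revision and label it as made after enrolment.

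The cost is wording, since the device-month monitoring is already part of the plan. What is lost is the before/after description within each condition, which has no contemporaneous reference in the second period.
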